8.3.2.5 Disease-Related Symptom Progression Rate

Disease-related symptom progression rate is defined as the proportion of randomized subjects who have disease-related symptom progression as measured by the FKSI-DRS.

The nine items of the FKSI-DRS are summarized into a symptom scale ranging in score from zero (0) to thirty six (36), with zero being the worst possible score and thirty six being the best possible score.⁵¹ The minimum important change in the FKSI-DRS used to define symptom progression is approximately a change of two points and that definition has been used for this mRCC symptom scale in other mRCC trials.^{40,51,52}

Disease-related symptom progression is defined as a decrease of two points in the FKSI-DRS relative to the subject's baseline FKSI-DRS score without returning to above that point during the remainder of the study.

FKSI-DRS questionnaire is completed at baseline, on Day 1 of each cycle (starting with cycle 2), and then at the X and XX follow-up visits.

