Study Design: This is a Phase 3, randomized, open-label study of nivolumab vs everolimus in subjects with advanced or metastatic RCC with a clear-cell component who have received at least one but not more than two prior anti-angiogenic therapy regimens in the advanced or metastatic setting and no more than three total prior systemic treatment regimens in the advanced or metastatic setting. Subjects must have evidence of progression on or after the last treatment regimen received and within 6 months prior to study enrollment. Approximately 822 subjects will be randomized 1:1 and stratified by region (US/Canada vs W. Europe vs Rest of World), Memorial Sloan-Kettering Cancer Center (MSKCC) risk group (favorable- vs intermediate- vs poor-risk; see [Appendix 1](#)), and number of prior anti-angiogenic therapy regimens in the advanced or metastatic setting (1 vs 2) to receive nivolumab (3 mg/kg IV every 2 weeks) on Arm A or everolimus (10 mg po daily) on Arm B. No dose increases or reductions will be allowed for nivolumab. Dose modifications for everolimus will be allowed as per the approved product label or as per standard practice in countries where everolimus is not approved for the treatment of advanced RCC. Subjects will be assessed for response (RECIST 1.1) by CT or MRI beginning 8 weeks after randomization and continuing every 8 weeks for the first year and then every 12 weeks until progression or treatment discontinuation, whichever occurs later. Subjects on both arms will be allowed to continue study therapy after initial investigator-assessed RECIST 1.1-defined progression if they are assessed by the investigator to be deriving clinical benefit and tolerating study drug. Such subjects must discontinue study therapy when further progression, as defined in the protocol, is documented. The primary endpoint of this study is OS. The final analysis of OS will occur after approximately 569 events (ie, deaths) have occurred. An interim analysis of OS will occur when at least 398 OS events (70% of total OS events needed for final analysis) have occurred. Objective response rate (ORR) and progression-free survival (PFS), each based on investigator assessments using RECIST 1.1 criteria, are key secondary endpoints that will be subject to hierarchical testing, with testing for ORR followed by testing for PFS if appropriate. Other secondary endpoints include duration of objective response, evaluation of PD-L1 as a predictive biomarker for OS, incidence of adverse events, serious adverse events, and specific laboratory abnormalities, and time to disease-related symptom progression rate.

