Laboratory Tests	X		For X01 (and XX01) ONLY, repeat at X02 (and XX02) if study drug related toxicity persists. To include CBC w/ differential, LFTs, BUN, creatinine, fasting serum lipids profile (total cholesterol, triglycerides, LDL, and HDL), fasting glucose, and TSH
Pregnancy Test	X		Serum or urine
Survival Status			
Subject Status	X	X	Every 3 months (Y and YY Survival Follow-ups may be accomplished by visit or phone contact), to include subsequent anti-cancer therapy.
Efficacy Assessments			
Tumor Assessments	X	X	Only for subjects without progression on study therapy. Tumor assessments should be continued every 8 wks (\pm 1 wk) from randomization (or first dose of nivolumab for the nivolumab extension phase) for the first 12 months, then every 12 weeks (\pm 1 wk) until disease progression is documented
Study Samples Arm A Only			
PK Samples	X		See Table 5.1-5; Only for subjects ORIGINALLY randomized to Arm A, not required for nivolumab extension phase
Immunogenicity Blood Sample	X		See Table 5.1-5; Only for subjects ORIGINALLY randomized to Arm A, not required for nivolumab extension phase

Table 5.1-4: Follow-Up Assessments (CA209025) - ALL Subjects			
Other			
Patient-Reported Outcome Measurements	X	X	Collect FKSI-DRS and EQ-5D at both “X” and “XX” follow-up visits Collect EQ-5D information either in person or via telephone at “Y” and “YY” survival visits, q3 months for 1 year, then q6 months (sect. 5.3.1)
Health Resource Utilization	X		

^a X visits as follow, X1 = 30 days from last dose \pm 7 days, or may be on date of discontinuation \pm 7 days if the date of discontinuation is more than 37 days after last dose. X2 = 100-121 days from last dose (ie, 70-84 days from X1); XX01 and XX02 follow the same timeframe, but from last dose from the nivolumab extension phase

^b Y, Survival visits continue every 3 months after X visits; YY, Survival visits continue every 3 months after the XX visits (nivolumab extension phase).

Table 5.1-5: Pharmacokinetic and Immunogenicity Sampling Schedule for Subjects Originally Randomized to the Nivolumab Arm				
Study Day^a	Time (Relative to Dosing) Hour	Time (Relative to Dosing) Hour: Min	Pharmacokinetic Blood Sample Schedule	Immunogenicity Blood Sample Schedule
Day -3 to +1 (post randomization)	0 (Predose)	00:00		X
Cycle 1 Day 1	1.0 (EOI) ^b	01:00	X	
Cycle 1 Dose 2	0 (Predose)	00:00	X	X
Cycle 2 Day 1	0 (Predose)	00:00	X	
Cycle 3 Day 1	0 (Predose)	00:00		
Cycle 4 Day 1	0 (Predose)	00:00	X	X

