5.3.1 Follow-up and Survival Procedures

Subjects will be monitored for safety according to [Table 5.1-4](#). During the 100 days after the last dose of study treatment, subjects will have two follow-up visits for safety. Safety assessments will include: review of concomitant medications, physical examination measurements, vital signs, performance status, laboratory measurements (CBC, serum chemistry, liver function and thyroid function), and assessment of signs and symptoms including AEs and SAEs. Beyond 100 days from the last dose of study treatment, subjects will be followed for ongoing drug-related adverse events until resolved, return to baseline or deemed irreversible, or until lost to follow-up, or withdrawal of study consent, or start of a subsequent anti-cancer therapy.

Blood samples will be collected for pharmacokinetics and immunogenicity as noted in [Table 5.1-5](#) (only for subjects randomized to nivolumab at the first 2 follow-up visits up to 100 days from the end of treatment, except for subjects that withdraw consent). For subjects treated in the nivolumab extension phase, blood samples for pharmacokinetics and immunogenicity will NOT be collected in the extension phase.

Patient reported outcome (PRO) assessments (FKSI-DRS and EQ-5D) will be administered at the first two follow-up visits prior to any study related procedures. Beyond the 100 days after discontinuation, the EQ-5D will be administered once every 3 months for the first 12 months, then once every 6 months thereafter, as permitted by local law. Each site will be provided with a touch screen electronic PC tablet for the subject's responses of the PRO questionnaire. Subjects will either enter the data directly on to the electronic PC tablet at the time office visits (direct contact) or will respond to the script version of the PRO questionnaire via telephone contact. If the responses are given by telephone, site personnel will enter the responses onto the PC tablet. The data will then be transferred to the ePRO vendor.

The PRO data collection will be according to [Table 5.1-4](#) until death, withdrawal of study consent, or lost to follow-up.

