8.4.6 Outcomes Research Analyses

FKSI-DRS questionnaire completion rate, defined as the proportion of questionnaires actually received out of the expected number (ie, the number of subjects still on treatment or in follow-up), will be calculated and summarized at each assessment point.

The disease-related symptom progression rate and its corresponding 95% exact CI will also be calculated by the Clopper-Pearson method for each randomized arm. The same analysis will be conducted, where death and radiographic progression will be also considered as disease-related symptom progression.

The EQ-5D will be used to assess each subject's overall health status. The following two measures from EQ-5D are used for this study: a population preference-based health state utility score (EQ-5D Index) and each subject's overall health state on a visual analog scale (EQ-VAS). Both the EQ-5D Index and EQ-VAS have been shown to be reliable and valid for assessing health-related PROs in cancer patients.

The health resource utilization data will be utilized to conduct economic analyses. ^{54,55,56}

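### The FKSI-DRS symptom progression rate is a crude proportion over an observation window that depends on treatment duration and survival, so the two arms' descriptive rates cannot safely be read side by side

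*Protocol*

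**What the plan says.** **Definition.** Section 8.3.2.5 of the protocol: "Disease-related symptom progression rate is defined as the proportion of randomized subjects who have disease-related symptom progression as measured by the FKSI-DRS". The event is a two-point fall from the subject's own baseline "without returning to above that point during the remainder of the study".

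**Collection.** The same section gives the schedule: "FKSI-DRS questionnaire is completed at baseline, on Day 1 of each cycle (starting with cycle 2), and then at the X and XX follow-up visits". Section 5.3.1 agrees: "Patient reported outcome (PRO) assessments (FKSI-DRS and EQ-5D) will be administered at the first two follow-up visits". A footnote to Table 5.1-4 times the second visit: "X2 = 100-121 days from last dose (ie, 70-84 days from X1". After that only the other instrument continues: "Beyond the 100 days after discontinuation, the EQ-5D will be administered once every 3 months for the first 12 months". The X visits follow the last dose of randomized treatment. The XX visits follow the last dose in the nivolumab extension phase.

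**Analysis.** Section 8.4.6: "The disease-related symptom progression rate and its corresponding 95% exact CI will also be calculated by the Clopper-Pearson method for each randomized arm". It then repeats the calculation with death and radiographic progression also counted as events.

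**Status.** Section 1.3.2 sets out to assess this rate in each arm, whereas the ORR and PFS objectives are worded as comparisons. Section 8.4.2 places only ORR and PFS in the hierarchy after OS.

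**Synopsis.** The Study Design paragraph lists the endpoint as "time to disease-related symptom progression rate". The synopsis analysis paragraph and Sections 1.3.2, 3.1, 8.3.2.5 and 8.4.6 all describe a rate.

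**The concern.** The denominator is everyone randomized, but the numerator can grow only while FKSI-DRS is being collected. That window has no fixed length. It ends about 100-121 days after the last dose, or at death if earlier, and treatment stops for progression, toxicity or other reasons. Two subjects with the same symptom course can therefore be classified differently because one was followed for longer. A subject who dies before any sustained drop is recorded stays in the denominator, with the same classification as one who stayed well.

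The exact binomial interval covers sampling error in the proportion and nothing else. In a randomized trial the two arm rates will be read next to each other whether or not a test is planned. If treatment duration or survival differs by arm, that reading mixes symptom risk with length of observation.

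The requirement that a drop persist to the end of the study can likewise be checked only up to the last questionnaire, so persistence is also judged over windows of unequal length.

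**Working it through.** The protocol states no expected rate, power or sample size for this endpoint, so there is no planned figure to reproduce. What follows is an illustration.

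**Inputs from the protocol**
- Median OS: 14.8 months (everolimus) and 19.5 months (nivolumab), Section 8.1.
- Subjects: about 822 randomized 1:1, so 411 per arm.
- End of FKSI-DRS: 100 days after last dose at the earliest, 100/30.4 = 3.3 months.

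**Assumptions (not in the protocol)**
- Exponential times.
- Median treatment of 4.9 months for everolimus. This borrows the everolimus median PFS of the earlier Phase 3 trial cited in Section 1.4.3; it is not a treatment duration.
- Median treatment of 8 months for nivolumab (10 months as a variant).
- Median time to symptom progression of 6, 12 or 24 months, **the same in both arms**.

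**Step 1: simple model, first drop is final.** Let λ, μ and τ be the hazards of symptom progression, death and stopping treatment (each ln 2 / median), and W = 3.3. Observation ends at treatment stop + W or at death. Then

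crude rate = λ/(λ+μ) × [1 − e^(−(λ+μ)W) × τ/(τ+λ+μ)]

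Example, symptom median 12, OS median 14.8, treatment median 4.9: λ = 0.0578, μ = 0.0468, τ = 0.1415, so 0.552 × [1 − 0.708 × 0.575] = 32.7%.

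| Symptom median (both arms) | Treatment 4.9, OS 14.8 | Treatment 8, OS 14.8 | Treatment 8, OS 19.5 |
|---|---|---|---|
| 6 months | 51.8% | 56.7% | 59.5% |
| 12 months | 32.7% | 37.5% | 40.0% |
| 24 months | 18.8% | 22.3% | 24.0% |

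The true symptom hazard ratio is 1 in every row. The gap is about 3.5 to 5 points from treatment duration alone and about 5 to 8 points when OS differs as well. For scale, with 411 subjects and a rate of 32.7% the Clopper-Pearson interval is 28.3% to 37.6%.

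**Step 2: deaths.** With treatment median 4.9 and symptom median 12, the crude rate is 41% if nobody dies, 32.7% at median OS 14.8 and 26% at median OS 7. Higher mortality lowers the apparent symptom rate. At median OS 14.8, 21% to 30% of subjects (symptom median 6 to 24 months) die inside the window without an event and count as not progressed.

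**Step 3: the protocol's sustained rule.** Step 1 treats the first drop as final, but Section 8.3.2.5 lets a subject recover and lose event status. A visit-level simulation (visits each cycle plus two follow-up visits, within-subject SD of 2 points assumed, median OS 14.8 in all cases) gives:

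| Mean drift per month | Treatment 4.9 | Treatment 8 | Treatment 12 |
|---|---|---|---|
| 0 | 28.3% | 28.3% | 28.2% |
| −0.1 | 38.6% | 40.4% | 41.5% |
| −0.3 | 52.9% | 55.6% | 57.3% |
| −0.5 | 61.0% | 63.1% | 64.4% |

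The direction is the same when symptoms worsen, but at 8 months' treatment the gap is only about 2 to 3 points. With no drift it disappears, because longer observation also allows recovery.

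**Step 4: would cumulative incidence alone cure it?** No. With an equal symptom hazard of 0.05 per month and death as a competing event, incidence at month 24 is λ/(λ+μ) × [1 − e^(−24(λ+μ))]:
- OS median 14.8: 0.05/0.0968 × (1 − e^(−2.324)) = 46.6%
- OS median 19.5: 0.05/0.0855 × (1 − e^(−2.053)) = 50.9%

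The arm that survives longer still shows more events. The cause-specific hazard ratio, which is 1 here, has to be reported beside it.

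**The case against.** **No comparison is planned.** This is correct. The objective is to assess each arm, the analysis is a per-arm rate with an interval, and the endpoint lies outside the hierarchy. A reader might infer that an error-controlled comparison is biased against nivolumab; the protocol contains no such comparison. What remains is the side-by-side reading of two descriptive rates.

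**Deaths are already handled.** In part. The second version in 8.4.6 counts death as an event, so early deaths are not ignored throughout. But it adds radiographic progression at the same time, which brings it close to a crude proportion of PFS events. It still ignores time and no longer isolates symptoms.

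**The size rests on the wrong model and on absent inputs.** Largely right. The protocol gives no expected treatment duration for either arm, does not say that durations will differ, and allows treatment beyond progression in both arms. The larger gaps come from a model without recovery. A reader might infer that the longer-treated arm must look worse, or that nivolumab would need a particular hazard ratio merely to tie. Neither is supported.

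**The synopsis phrase shows nothing about intent.** Agreed. It stands alone against consistent wording elsewhere and is a drafting inconsistency to reconcile.

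**The SAP may add a time-to-deterioration analysis.** It may, and its absence here is no fault. The protocol itself, however, fixes the endpoint as a proportion over a variable window, and that is the point at issue.

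**Conclusion.** The concern holds as a limit on interpretation. As defined, the arm rates depend on how long FKSI-DRS was collected and on who died first, as well as on symptoms. If treatment duration or survival differs by arm, they are not comparable. That dependence follows from Sections 8.3.2.5, 8.4.6 and 5.3.1 and Table 5.1-4 without further assumption.

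The size is uncertain: about 0 to 8 points at identical symptom hazards. The upper end comes from the model without recovery and with unequal OS; the sustained rule shrinks the gap, and it is nil with no drift. Treatment durations, symptom hazards, drift and within-subject SD are all assumed. The direction, a higher rate in the longer-observed arm, is a tendency when symptoms worsen over time and not a certainty. Type I error and the OS, ORR and PFS tests are untouched.

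**What to change.** In Sections 8.3.2.5 and 8.4.6:

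1. Analyse time from randomization to the first sustained FKSI-DRS drop of at least two points.
2. Report the cause-specific hazard ratio, stratified by region, MSKCC risk group and number of prior anti-angiogenic regimens, as descriptive and outside the testing hierarchy. Give with it the cumulative incidence by arm, treating death as a competing event.
3. State three rules: censoring at the last FKSI-DRS assessment; how to treat a first drop that falls on the last available score; and exclusion of extension-phase (XX) scores of everolimus subjects, which would otherwise be scores under nivolumab credited to the everolimus arm.
4. Keep the crude proportion as a descriptive line.
5. Reconcile the synopsis phrase "time to disease-related symptom progression rate" with Section 8.3.2.5.

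The cost is wording and a little programming; the questionnaires and schedule do not change. The drawback is that censoring when collection ends may be informative, since treatment often stops for progression or toxicity. The text should say so and add, for example, a sensitivity analysis counting death as an event.

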With this amendment, all subjects randomized to the everolimus treatment Arm B who meet eligibility criteria may enter the nivolumab extension phase, according to the schema below. These subjects will follow the assessment schedules outlined in [Table 5.1-7](#) and [Table 5.1-8](#) of the protocol.

Subjects treated with everolimus who have ended study treatment will be able to receive treatment with nivolumab via the extension phase of the study, assuming basic eligibility criteria are met (including a 14-day washout period for prior systemic anti-cancer therapy). Details are provided in [Sections 3.3.1.1](#) and [3.3.2.1](#).

Subjects currently receiving treatment with everolimus may continue to be treated and monitored as specified in the protocol as long as they are continuing to derive benefit from everolimus in the judgment of the investigator. These subjects may receive nivolumab once they are discontinued from everolimus therapy, assuming basic eligibility criteria are met (including a 14-day washout period from the last dose of everolimus).

Nivolumab Extension Phase (schema for those previously randomized to everolimus):

*Treatment beyond investigator-assessed RECIST 1.1-defined progression may be considered for subjects meeting criteria according to [Section 4.3.6](#). Treatment beyond progression for subjects in the nivolumab extension phase must be approved by the BMS Medical Monitor or Study Director prior to subjects receiving additional study drug. Criteria for discontinuation of treatment beyond progression are described in [Section 4.3.6](#).

Treatment Phase:

- Begins with the randomization call to the IVRS. The subject is randomly assigned to either the nivolumab arm (Arm A) or the everolimus arm (Arm B).

- Within 3 working days from randomization the subject must receive the first dose of study medication (Day 1 of Cycle 1).
- On-study labs (cycle 2 and beyond) should be drawn within 72 hours prior to re-dosing. Adverse event assessments should be documented at each clinic visit and women of childbearing potential (WOCBP) must have a pregnancy test at every new cycle visit.
- PK samples, immunogenicity and serum for soluble factors samples for subjects on nivolumab (Arm A) will be done according to the schedule in [Table 5.1-5](#). and a single serum soluble factor sample for subjects on Arm B will be done according to [Table 5.1-6](#).

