- b) WOCBP must have a negative serum or urine pregnancy test (minimum sensitivity 25 IU/L or equivalent units of HCG) within 24 hours prior to the start of investigational product.
- c) Women must not be breastfeeding.
- d) Men who are sexually active with WOCBP must use any contraceptive method with a failure rate of less than 1% per year. Men that are sexually active with WOCBP must follow instructions for birth control when the half life of the investigational drug is greater than 24 hours, contraception should be continued for a period of 90 days plus the time required for the investigational drug to undergo five half lives. For men randomized to receive nivolumab, this is equivalent to 31 weeks after discontinuation of treatment. Men randomized to receive everolimus must follow instructions for birth control for 14 weeks after discontinuation of treatment.

4) Physical and Laboratory Test Findings

- a) Serum creatinine $\leq 1.5 \times \text{ULN}$ OR CrCl ≥ 40 mL/min (measured or calculated using the Cockcroft-Gault formula):

$$\text{Female CrCl} = \frac{(140 - \text{age in years}) \times \text{weight in kg} \times 0.85}{72 \times \text{serum creatinine in mg/dL}}$$

$$\text{Male CrCl} = \frac{(140 - \text{age in years}) \times \text{weight in kg} \times 1.00}{72 \times \text{serum creatinine in mg/dL}}$$

3.3.1.1 ***Inclusion Criteria for Entering the Nivolumab Extension Phase - Subjects Previously Randomized to Everolimus***

1) Signed Written Informed Consent

- a) Subjects must have signed and dated an IRB/IEC approved written Informed Consent Form in accordance with regulatory and institutional guidelines. This must be obtained before the performance of any protocol-related procedures that are not part of normal subject care.
- b) Subjects must be willing and able to comply with scheduled visits, treatment schedule, laboratory tests and other requirements of the study.

2) Target Population

- a) Subjects previously randomized to everolimus treatment (Arm B) on the CA209025 study.
- b) Prior anti-cancer therapy, including everolimus and palliative radiotherapy, must have been completed at least 14 days prior to first dose of nivolumab.
- c) All toxicities attributed to prior anti-cancer therapy other than alopecia and fatigue must have resolved to Grade 1 or baseline prior to first dose of nivolumab.
- d) Laboratory values must meet the following criteria and should be obtained within 14 days prior to first dose of nivolumab:

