Administer Study Treatment	X	X		Record study drug infusion start and stop times for nivolumab. Doses of nivolumab should not be given less than 12 days from the previous dose. If the 2nd dose cannot be given within a 28 day window, it will be omitted and the next dose received will be Day 1 of the next cycle.
Other				
Patient-Reported Outcome Measurements	X			Prior to any study-related procedures: FKSI-DRS and EQ-5D
Health Resource Utilization	X			Except cycle 1. (Section 5.8.1)

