8.3.2.4 Safety

Safety will be analyzed through the incidence of adverse events, serious adverse events and specific laboratory abnormalities (worst grade) in each treatment arm. Toxicities will be graded using the National Cancer Institute (NCI) Common Terminology Criteria for Adverse Events (CTCAE) version 4.0.

Adverse event assessment is performed on an ongoing basis while on treatment and for up to 100 days after the last dose of study drug (ie, during the X follow-up visits).

Laboratory tests are performed at baseline, on Day 1 of each cycle (within 72 hours prior to dose for all cycles except 1 (see [Table 5.1-2](#)), and at the first visit in follow-up. Tests at second visit in follow-up will be repeated if study drug related toxicity persists.

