8.4.2.1 Methods of Primary Endpoint

The OS distributions will be compared in two randomized arms at the interim and final analyses via two-sided, log-rank tests, stratified by region, MSKCC risk group, and number of prior anti-angiogenic therapy regimens in the advanced or metastatic setting. The interim analysis for OS is planned after 398 deaths have been observed. This formal comparison of OS will allow for early stopping for efficacy and the stopping boundaries will be derived based on the O'Brien and Fleming alpha spending function in EAST v5.4. If the analysis is performed exactly at 398 events, the study could be stopped by the DMC for efficacy if the p-value is ≤ 0.0148 . The nominal significance level for the final look of OS after 569 events would then be 0.0455. The OS curve, median and OS rates at 12, 18, and 24 months for each randomized arm will be estimated using the Kaplan-Meier product-limit method. Two-sided, 95% confidence intervals for median OS will be computed by Brookmeyer and Crowley method.⁵³ Similarly, two-sided, 95% confidence intervals for OS rates at 12, 18, and 24 months will be computed by Greenwood method. The hazard ratio (HR) and corresponding two-sided 100(1- α)% (adjusted for the interim analysis) CI will be estimated in a Cox proportional hazards model using randomized arm as a single covariate, stratified by the above factors.

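### The FKSI-DRS endpoint in Section 8.3.2.5 lets scores taken on or after extension-phase nivolumab decide an everolimus-arm subject's symptom progression status

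*Protocol*

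**What the plan says.** **Crossover.** Protocol Section 3.1 (Amendment 15 update) states that "all subjects randomized to the everolimus treatment Arm B who meet eligibility criteria may enter the nivolumab extension phase". Section 3.3.1.1 sets the earliest entry: "Prior anti-cancer therapy, including everolimus and palliative radiotherapy, must have been completed at least 14 days prior to first dose of nivolumab".

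**What XX visits are.** Footnote a of Table 5.1-4 separates them from X visits: "XX01 and XX02 follow the same timeframe, but from last dose from the nivolumab extension phase". Only a subject randomized to everolimus who later took extension nivolumab can have one.

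**FKSI-DRS endpoint.** Section 8.3.2.5 defines a proportion of randomized subjects. Progression is a 2-point fall from the subject's baseline "without returning to above that point during the remainder of the study". The questionnaire is completed at baseline, "on Day 1 of each cycle (starting with cycle 2), and then at the X and XX follow-up visits". Section 8.4.6 gives the rate and an exact confidence interval for each randomized arm. Tables 5.1-7 and 5.1-8 collect the FKSI-DRS at extension screening and on Day 1 of each extension cycle ("Prior to any study-related procedures: FKSI-DRS and EQ-5D").

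**Safety window.** Section 8.3.2.4 has adverse events assessed "while on treatment and for up to 100 days after the last dose of study drug", and adds that this means the X visits. Table 5.1-4 continues collection to X02 or XX02. Section 8.2 defines treated subjects by any dose of either drug, without splitting by period.

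**The concern.** The symptom progression rate is a named secondary objective (Section 1.3.2), meant to describe each randomized treatment. Once Arm B subjects receive nivolumab, their later scores reflect everolimus followed by nivolumab. The wording brings those scores into the everolimus-arm rate in two ways: through the visit list, and through a persistence condition that runs to the end of the study. Section 3.1 allows survival follow-up for up to 5 years after the primary analysis, so the condition can stay open for a long time.

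The assessment period also becomes unequal. After X2, Table 5.1-4 collects only the EQ-5D at survival visits, so an Arm A subject's FKSI-DRS series ends there. An Arm B subject who enters the extension has the series resumed through extension cycles and XX visits. Arm A has no counterpart to that second period.

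**Working it through.** The protocol gives no rate, power or precision for this endpoint, so there is no figure to reproduce. The check is of the text, followed by an illustration of scale.

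**1. Whose status can XX data change?** Only Arm B subjects have XX visits (Table 5.1-4, footnote a). The endpoint is counted over randomized subjects and reported by randomized arm. XX data therefore enter one arm only, and always after nivolumab.

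**2. Would deleting XX be enough?** No. Extension cycles also have a Day 1 FKSI-DRS (Table 5.1-8), and the persistence condition has no stop at the first extension dose. Both parts of the definition need a limit.

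**3. Direction.**
- A subject who fell by 2 points on everolimus and regains the level on nivolumab changes from progressed to not progressed.
- A subject who had not fallen on everolimus but falls on nivolumab changes from not progressed to progressed.

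The error can go either way.

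**4. Which outputs are exposed?** The Data Monitoring Committee reviewed the interim data on 17-Jul-2015. The extension came with the amendment of 12-Aug-2015. The interim results, now the final primary results, contain no extension data. Only later outputs are exposed.

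**5. Scale, as an illustration.** The largest pool that could cross over is the everolimus subjects still alive. Inputs from Section 8.1: 822 subjects randomized 1:1 (411 per arm), everolimus median OS 14.8 months, HR 0.76, 20 months of accrual, 398 deaths. Assumed here: exponential survival and uniform accrual.

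- λ = ln 2 / 14.8 = 0.0468 per month. Alive at time T = 411 × [exp(−λ(T − 20)) − exp(−λT)] / (20λ).
- Under this model 398 deaths occur at T = 26.8 months, with about 194 everolimus subjects alive (212 if HR = 1). At the protocol's projected 30 months the model gives 167.

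Take 190 alive. Assume 10–50% enter the extension, 40–60% of them have already met the drop, 10–50% of those regain the level on nivolumab, and 0–20% of the others newly fall. None of these four rates is in the protocol.

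- Largest decrease: 190 × 0.50 = 95 enter; 95 × 0.60 × 0.50 = 28.5 progressions cancelled; 28.5 / 411 = 6.9 points down.
- Largest increase: 95 × 0.40 × 0.10 = 3.8 cancelled and 95 × 0.60 × 0.20 = 11.4 added; (11.4 − 3.8) / 411 = 1.8 points up.

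The shift is proportional to the pool, so 167 or 212 alive rescales both ends by 0.88 or 1.12.

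**6. Safety overlap.** The window after everolimus is 100 days and the minimum gap before extension nivolumab is 14 days, so at most 100 − 14 = 86 days can overlap. A subject entering more than 100 days after the last everolimus dose has none.

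**The case against.** **The endpoint carries little inferential weight.** It is outside the testing hierarchy of Section 8.4.2 and is reported as a rate per arm without a between-arm test. Section 8.4.6 also repeats the analysis counting death and radiographic progression, which later recovery on nivolumab cannot undo. Both points stand and limit the consequence. They do not repair the main definition.

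**Following subjects by randomized arm regardless of later treatment is legitimate.** It would be if applied evenly. Here only extension nivolumab brings further FKSI-DRS collection; subjects who move to other therapy have no FKSI-DRS after X2.

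**The statistical analysis plan may set a cut-off.** It may, and it is not at hand. It would then depart from what Section 8.3.2.5 states, so the protocol wording needs correcting in either case.

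A reader might also infer more than the text supports:

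- *That nivolumab adverse events are assigned to everolimus.* Section 8.3.2.4 limits its window to the X visits, and no section assigns extension events to the everolimus arm. What remains is an overlap of up to 86 days for prompt switchers with no stated split, and a difference from Table 5.1-4. Multiplying the 14% Grade 3/4 rate in Section 1.4.5.1 by a crossover fraction would not size it: that is a cumulative rate from a multi-tumor Phase 1 study, and the crossover fraction would be a guess.
- *That every secondary endpoint is contaminated.* Best response stops at subsequent therapy (Section 8.3.2.1), and PFS is censored before it (Section 8.3.2.2). Duration of response takes its censoring date from PFS (Section 8.3.2.3).
- *That a formal OS test on crossover data is still planned.* Section 8.4.2.1 retains "The nominal significance level for the final look of OS after 569 events would then be 0.0455", but the Synopsis and Section 3.1 make the interim results final. The leftover wording is editorial.
- *That everolimus symptom progression would be understated.* Step 3 of the working shows that the direction is not fixed.

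**Conclusion.** The point holds for the FKSI-DRS endpoint. Section 8.3.2.5, read with Table 5.1-4 and Section 8.4.6, lets scores taken on or after extension nivolumab decide the status of everolimus-arm subjects, in either direction, in any output produced after the extension opens. It also gives those subjects an assessment period that Arm A lacks. The results declared final, the primary endpoint and the two tested secondary endpoints are not affected.

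The size cannot be obtained from the protocol. The range of about -6.9 to +1.8 percentage points rests on the assumed entry, progression, recovery and new-decline rates, on exponential survival and on uniform accrual; it shows scale and is not an estimate. For safety the finding is a missing period rule, not a stated misattribution. Overall this is a modest defect in a descriptive secondary endpoint, worth correcting before the FKSI-DRS is next reported.

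**What to change.** - **Section 8.3.2.5.** For the randomized comparison, remove XX visits from the assessment list. State that Arm B scores count only up to the first extension dose of nivolumab, and that the persistence condition ends there for subjects who enter the extension.
- **Extension-phase FKSI-DRS.** Report it separately, with the screening score taken before the first extension dose (Table 5.1-7) as its own baseline.
- **Section 8.3.2.4, a lesser clarification.** State that the everolimus-arm adverse event and laboratory summaries stop at the first extension dose when it falls within 100 days of the last everolimus dose, and tabulate extension-phase events separately.

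The cost is a few sentences and one extra set of extension-phase tables. No new data are needed and no treatment rule changes. One consequence should be stated with the results: for subjects who switch promptly, the cut removes some post-everolimus scores, so a drop not yet regained at the first extension dose counts as progression.
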